2.5 Correlative Studies Background

Cohort 1: In this cohort, patients with recurrent GBM will receive drug for 10-14 days prior to a reoperation. Tumor will be resected and analyzed for:

- 1) Pre-treatment tumor will be genotyped with next generation sequencing and the results correlated with outcome if not previously performed.
- 2) Drug concentration using liquid chromatography tandem mass spectrometry (LC-MS/MS). Tumor concentration will be compared to plasma drug concentrations to determine if therapeutic levels of abemaciclib can be achieved in both enhancing and non-enhancing tumor.
- 3) Tumor tissue will be analyzed by IHC and proteomics analysis for Phospho-Rb, (S807/811) proliferation (Ki-67), and apoptosis (cleaved caspase 3) to determine if abemaciclib can achieve a pharmacodynamic effect in enhancing and non-enhancing tumor tissue. These data will be compared to results from the patient's prior archived tumor tissue not exposed to abemaciclib obtained from each participant's prior surgery, and to results from unrelated glioblastoma patients (n=10) with tumor tissue from preand post-treatment with standard of care RT+TMZ.
- 4) Tumor tissue will be analyzed for quantitative assessment of TIL that express PD-1, delineation of PD-L1+ cells in the tumor microenvironment (macrophage vs. tumor cells), immune response based multiplex gene expression analysis in tumor samples preand post-treatment, and quantitative assessment of T cell receptors in tumor samples preand post-treatment
- 5) Tumor tissue will be analyzed for tumoral expression of major histocompatibility complex type I and II, markers of T-cell exhaustion, type III interferon production and profiling of the immune milieu of the tumor microenvironment by multiplexed immunofluorescence (IF), and activation of abemaciclib-induced intrinsic anti-tumor immunity by gene expression analysis.
- 6) If sufficient tumor is available, fresh patient derived cells (PDC), patient-derived cell lines (PDCL), and patient derived xenografts (PDX) will be attempted to be generated.
- 7) Fresh cells or PDCL/PDX models will undergo functional sensitivity testing to abemaciclib or studied using genomics or expression analysis.

Cohort 2: Tumor from the participant's surgery prior to enrolling onto the study will be studied for correlative markers.

- 1) Pre-treatment tumor will be genotyped with next generation sequencing and the results correlated with outcome if not previously performed.
- 2) IHC analysis of pRB, Ki67, and CC3 will be performed for correlation with outcome.
- 3) Analysis of any cell lines derived from prior surgery will be studied if available.

3. PARTICIPANT SELECTION

Screening evaluations are detailed in Study Calendar (Section 10). All assessments are to occur within 14 days of registration except where otherwise noted. The participant must be thoroughly informed of all aspects of the study, including the study visit schedule and required evaluations and all regulatory requirements for informed consent. The written informed consent must be obtained from the participant prior to enrollment.

Following registration, any additional laboratory assessments obtained prior to start of treatment will not be used to re-confirm eligibility. Please refer to Section 6.2 and Table 6.3 Dosing Delays/Dose Modifications for toxicity management between registration and start of study treatment.

3.1 Eligibility Criteria

All participants must meet the following criteria on screening examination to be eligible to participate in the study:

- 1. Participants must be able to understand and willing to sign a written informed consent document.
- 2. Participants must be able to adhere to the dosing and visit schedules and agree to record medication times accurately and consistently in a daily diary.
- 3. Participants must be at least 18 years old on day of signing informed consent.
- 4. Participants must have a Karnofsky Performance Status (KPS) \geq 60 (see Appendix A).
- 5. Participants must be able to swallow tablets.
- 6. Participants with a prior or concurrent malignancy whose natural history or treatment does not have the potential to interfere with the safety or efficacy of the trial are eligible.
 - NOTE: consultation with the Overall PI is highly recommended if enrollment of a participant with a prior or concurrent malignancy is being pursued.

Nature of illness and treatment history

- 7. Participants must undergo central pathology review to histologically confirm the diagnosis of glioblastoma, IDH-wildtype; glioblastoma variants; or astrocytoma, IDH-mutant, WHO grade 4 (1 unstained slide or 1 H&E slide must be submitted to and reviewed by a pathologist at the DFCI Coordinating Center prior to enrollment of the participant for central pathology review).
- 8. To be eligible for the study all participants (Cohort 1 and 2) are required to provide genomic profiling data from assays performed in a CLIA-certified lab. A sequencing-based assay is required and must include reporting of the RB1 gene in explicit terms within the report. Only sequencing assays that include coverage of *all* exons of the RB1 gene are able to be utilized (most commonly called a targeted exome assay; e.g. Oncopanel, Impact, FoundationOne). In addition, patients must provide a report of copy

assessment which reports status of RB1. The reporting may be from a copy array (ideally Oncoscan SNP array or Agilent array CGH) or can also be from sequencing assay if copy status is explicitly provided with quantitative information regarding the status of relevant genes. Specifically, the reporting should provide the following information with respect to relevant biomarkers required for enrollment to the study as listed below.

Results from genomic profiling must be sent to the DFCI Coordinating Center prior to enrollment of the participant for central pathology review. Central pathology can provide feedback on reports if requested to help in assessing status as needed.

o Inactivation of CDKN2A/B or C in the tumor by homozygous deletion (evidence for more than single copy loss for any of the genes defined as array CGH/SNP log2 ratio of <0.3 by array CGH; or from sequencing data with sufficient coverage for evaluation). Rearrangement/evidence or intragenic breaks by copy or sequencing assay also will be considered eligible for study (any copy status).

OR

o CDK4 or CDK6 high-level amplification. (The amplicon size must be <10Mb and the magnitude the gain must be log2 ratio >1.5 or estimated as >10 copies).

AND

- Validation of wild-type RB status (no deletion/losses more than single copy by copy number or sequencing data; and/or no inactivating mutations or rearrangements by sequencing).
- 9. Participants must be at first or second relapse of GBM. Relapse is defined as progression following therapy. The intent is that patients had no more than 2 prior therapies.
- 10. Participants must have shown unequivocal evidence for tumor progression by MRI or CT scan.
 - o For Cohort 2 subjects, CT or MRI within 14 days prior to study registration. For Cohort 2, corticosteroid dose must be stable or decreasing for at least 5 days prior to the scan. If steroids are added or the steroid dose is increased between the date of the screening MRI or CT scan and the start of treatment, a new baseline MRI or CT is required.
 - o For Cohort 1 subjects, CT or MRI should be performed ideally within 14 days prior to study registration, but because the screening MRI for this subset of subjects will not be used for evaluation of response, it is acceptable for this MRI/CT to have been performed greater than 14 days prior to registration if unavoidable. Furthermore, for this same reason, fluctuation in corticosteroid dose around this MRI does not warrant repeat scan so long as there is documented unequivocal evidence of tumor progression available.
 - For Cohort 1 subjects, there must be > 2cm² enhancing tissue available for resection and submission for study correlatives as determined by local treating team.
- 11. Confirmation of availability of sufficient tissue from a prior surgery for correlative

studies is required prior to enrollment; these samples must be sent to the DFCI Coordinating Center within 60 days of registration. Cohort 1 participants must have sufficient FFPE tissue from any surgery. Cohort 2 participants must have tissue from biopsy or resection from the most recent recurrence surgery.

The following amount of archived tissue is required:

o 20 unstained formalin fixed paraffin embedded (FFPE) sections (standard 5 micrometer thickness)

NOTE: if the above-mentioned tissue is not available from the most recent surgery revealing GBM, participants may be enrolled with tissue available from any prior surgery revealing GBM with prospective approval from the Overall PI.

- 12. An interval of at least 12 weeks from the completion of radiation therapy to start of study drug unless there is a new area of enhancement consistent with recurrent tumor outside the radiation field (defined as the region outside the high-dose region or 80% isodose line) or there is unequivocal histologic confirmation of tumor progression. If recurrence is outside the radiation field or there is histologic confirmation of tumor progression, then an interval of at least 14 days must have elapsed from completion of radiation therapy to start of study drug and participants must have fully recovered from the acute effects of radiotherapy.
- 13. Participants must have recovered to grade 0 or 1 or pre-treatment baseline from clinically significant toxic effects of prior therapy (including but not limited to exceptions of alopecia, laboratory values listed per inclusion criteria, and lymphopenia which is common after therapy with temozolomide).
- 14. From the projected start of scheduled study treatment, the following time periods must have elapsed:
 - o 4 weeks or 5 half-lives (whichever is shorter) from any investigational agent;
 - 4 weeks from cytotoxic therapy (except 23 days for temozolomide; 6 weeks from nitrosoureas);
 - o 4 weeks from antibodies;
 - o 4 weeks or 5 half-lives (whichever is shorter) from other anti-tumor therapies.
 - o 2 days from Novo-TTF
- 15. Participants with prior therapy that included interstitial brachytherapy or stereotactic radiosurgery must have confirmation of progressive disease based upon nuclear imaging, MR spectroscopy, perfusion imaging or histopathology.
- 16. Participants having undergone recent resection or open biopsy or stereotactic biopsy of recurrent or progressive tumor will be eligible for Cohort 2 as long as the following conditions apply:
 - o They have recovered from the effects of surgery.
 - Residual disease following resection of recurrent tumor is not mandated for eligibility. To best assess the extent of residual disease post-operatively, an MRI

or CT scan should ideally have been performed no later than 96 hours following surgery, or at least 28 days post-operatively, but scans performed outside of this window are considered acceptable if no alternative is available. In either case, the baseline/screening MRI must be performed within 14 days prior to registration. If the participant is taking corticosteroids, the dose must be stable or decreasing for at least 5 days prior to the scan. If steroids are added or the steroid dose is increased between the date of the screening MRI or CT scan and the start of treatment, a new baseline MRI or CT is required.

Clinical labs – performed within 14 days prior to registration

17. Hematology:

- Absolute neutrophil count (ANC) \geq 1.5 x K/ μ L
- Platelet count $\geq 100 \text{ x K/}\mu\text{L}$
- Hemoglobin $\ge 8.0 \text{ g/dL}$

18. Biochemistry:

- o Total serum calcium (corrected for serum albumin as needed) or ionized calcium within institution's normal range.
- o Magnesium within institution's normal range.
- o AST (SGOT) and ALT (SGPT) \leq 3.0 x institution's ULN
- Serum bilirubin \leq 1.5 x institution's ULN. Patients with Gilbert's syndrome with a total bilirubin \leq 2.0 times ULN and direct bilirubin within normal limits are permitted.
- o Serum creatinine ≤ 1.5 x institution's ULN or calculated 24-hour creatinine clearance ≥ 50 mL/min
- Serum amylase ≤ 1.5 x institution's ULN
- Serum lipase ≤ 1.5 x institution's ULN

19. Coagulation studies:

- o INR < 2.0
- o PTT ≤ institution's ULN, unless receiving therapeutic low molecular weight heparin or oral factor Xa inhibitors.

Pregnancy and Reproduction

20. Based on findings in animals, abemaciclib can cause fetal harm when administered to a pregnant woman. For this reason, women of child-bearing potential (WOCBP) must agree to use a highly effective contraceptive method during the treatment period and for 3 weeks following the last dose of abemaciclib. Men must agree to use a reliable method of birth control and to not donate sperm during the study and for at least 3 weeks following the last dose of abemaciclib. Contraceptive methods may include an intrauterine device [IUD] or barrier method. If condoms are used as a barrier method, a spermicidal agent should be added as a double barrier protection.

- o NOTE: Women are considered post-menopausal and not of child bearing potential if they have had 12 months of natural (spontaneous) amenorrhea with an appropriate clinical profile (e.g., age appropriate, history of vasomotor symptoms) or six months of spontaneous amenorrhea with serum FSH levels > 40 mIU/mL and estradiol < 20 pg/mL or have had surgical bilateral oophorectomy (with or without hysterectomy) at least six weeks ago. In the case of oophorectomy alone, only when the reproductive status of the woman has been confirmed by follow up hormone level assessment is she considered not of child bearing potential.
- 21. Women of child-bearing potential must have a negative serum pregnancy test within 7 days prior to first dose of abemaciclib.

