9.1 Biomarker Studies from Any Prior Surgery

Eligibility for registration will be dependent on prior tumor being profiled by genomic methods that are sufficient for determination of the copy and mutation status of CDKN2A/B/C, RB1, and CDK4/6. Data can be generated from any prior tumor surgery. This data will not be generated as part of the trial process but will be pre-existing data. All data must be performed in a CLIA-certified laboratory. Central molecular pathology review will be performed and may include reports or raw data as needed to determine the status of relevant loci. Commonly used tests include:

- 1. OncoCopy Whole Genome Array CGH (DFCI/BWH)
- 2. OncoPanel Targeted Exome Sequencing (DFCI/BWH)
- 3. FoundationOne testing (Foundation Medicine)
- 4. Other sequencing and copy data (e.g. TGEN)
- 5. IMPACT sequencing and copy (MSKCC)

Data will be evaluated for:

1. Presence of CDKN2A, CDKN2B, CDKN2C loss equivalent to a loss greater than 1 copy of any one or more of these genes. Entry based on single copy loss will be allowed only in the event of a concurrent SNV present which is deemed likely damaging/inactivating by literature and database review.

AND

2. Absence of any copy, SNV, indel, or other aberration deemed likely inactivating in the RB1 gene. These would include non-sense mutations with truncation of protein, or homozygous (>1 copy) loss by copy analysis.

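### Criterion 8's array cut-off does not define the CDKN2A/B/C loss it names, and sections 3.1, 9.1 and 14.1 give different entry routes

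*Combined protocol and SAP*

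**What the plan says.** Section 3.1, criterion 8, applies to both cohorts. It asks for homozygous deletion of CDKN2A/B or C and, for arrays, gives the definition "evidence for more than single copy loss for any of the genes defined as array CGH/SNP log2 ratio of <0.3 by array CGH". Sequencing data may be used instead, with no numeric cut-off. Two further routes follow: "Rearrangement/evidence or intragenic breaks by copy or sequencing assay also will be considered eligible for study (any copy status") and, as an alternative, "CDK4 or CDK6 high-level amplification" subject to limits on amplicon size and gain. Each route also needs wild-type RB, described by a copy-number condition followed by "and/or no inactivating mutations or rearrangements by sequencing". On central handling, "Results from genomic profiling must be sent to the DFCI Coordinating Center prior to enrollment".

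Section 9.1 opens by requiring prior profiling "sufficient for determination of the copy and mutation status of CDKN2A/B/C, RB1, and CDK4/6". Its first numbered condition is "Presence of CDKN2A, CDKN2B, CDKN2C loss equivalent to a loss greater than 1 copy of any one or more of these genes", and it adds: "Entry based on single copy loss will be allowed only in the event of a concurrent SNV present which is deemed likely damaging/inactivating". Its second condition is the absence of any likely inactivating RB1 aberration. It states that central molecular review will take place and may draw on raw data.

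Section 14.1 gives the purpose of central review as confirming histology, CDKN2A/B loss and intact RB. Sections 1.1 and 2.3 describe the population in the same terms. Section 2.4 reports that Cohort 2 has completed accrual, with PFS6 of 9.37%, and that Cohort 1 still has open slots.

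**The concern.** A numeric definition should separate the state it names from the neighboring state. Here the neighbor is single-copy loss, which 9.1 accepts only with a second damaging hit. The cell-line work in section 2.2 ties sensitivity to homozygous deletion or loss of more than one copy. If the number lets single-copy loss through, the array rule selects a broader group than the biomarker rationale describes.

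The entry routes are a second, separate matter. A tumor with CDK4 amplification and no CDKN2A/B loss meets criterion 8, yet lacks what 14.1 tells the central reviewer to verify. A tumor with single-copy loss plus SNV is in the reverse position between 9.1 and criterion 8.

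Two things are at stake. The genotype mix behind the remaining Cohort 1 pharmacodynamic results (pRB, Ki67) depends on how these texts are applied. And a reader of the Cohort 2 PFS6 cannot tell which entry routes it covers, because the documents do not say how patients qualified.

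**Working it through.** **The plan's own figures.** Section 13.3 gives n = 32, success at 8 or more, and rates of 15% and 35%. Exact binomial: P(X ≥ 8 | 32, 0.35) = 0.918 (stated 0.92) and P(X ≤ 7 | 32, 0.15) = 0.904 (stated 0.90). Both reproduce, and neither depends on this point.

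**The cut-off: inputs.** The value 0.3 comes from criterion 8. The minimum of 50% tumor nuclei comes from section 9.2.1.1 (the DFCI/BWH array assay). The assumptions, which are not in the documents, are a near-diploid tumor, a clonal event and normal cells with two copies.

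**Formula.** With tumor content p and c copies in tumor cells, mean copies = p·c + 2(1 − p), and log2 ratio = log2(mean copies / 2). Single-copy loss (c = 1) gives log2(1 − p/2). Homozygous loss (c = 0) gives log2(1 − p).

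**As printed (< 0.3).** The boundary is 2 × 2^0.3 = 2.46 mean copies. A two-copy gene has log2 ratio 0 at every tumor content, so it qualifies.

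**With a minus sign (< −0.3).** The boundary is 2 × 2^(−0.3) = 1.62 mean copies. Single-copy loss passes when p > 2(1 − 2^(−0.3)) = 0.375. Homozygous loss passes when p > 1 − 2^(−0.3) = 0.188.

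| Tumor content | Single-copy loss | Homozygous loss |
|---|---|---|
| 40% | −0.322 | −0.737 |
| 50% | −0.415 | −1.000 |
| 70% | −0.621 | −1.737 |
| 80% | −0.737 | −2.322 |
| 100% | −1.000 | no finite value |

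Every entry in the single-copy column is below −0.3. The cut-off therefore catches true homozygous deletions but does not exclude the neighboring state. For p of 50% or more, single-copy loss lies between −1.0 and −0.415 and homozygous loss is at or below −1.0. The two ranges touch at −1.0 with no gap.

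**The entry routes, side by side.**

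| Route | 3.1, criterion 8 | 9.1, numbered conditions | 14.1, 1.1 and 2.3 |
|---|---|---|---|
| CDKN2A/B loss beyond one copy | yes | yes | loss named, extent not given |
| CDKN2C loss beyond one copy | yes | yes | not named |
| Rearrangement or break, any copy number | yes | not listed | not named |
| CDK4/6 amplification | yes | not listed (named in the lead-in) | not named |
| Single-copy loss plus damaging SNV | not listed | yes | extent not given |

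This comparison needs no model.

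**The case against.** The strongest reply is that the number does not stand alone. Criterion 8 surrounds it with the words homozygous deletion, 9.1 repeats the requirement, and a central molecular reviewer with access to raw data will look at each case. Section 3.1 is the operative list, registration uses an eligibility checklist built on it, and Appendix B section 3.7.3 bars exceptions without IRB approval. Sections 1.1 and 2.3 are summary and rationale. This stands as a limit on the practical effect. It does not repair the text: criterion 8 makes the number the definition, and 14.1 tells the reviewer to verify something that criterion 8 does not always require.

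Several stronger readings are tempting, and the documents do not support them.

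- *The protocol has a sign error and admits unaltered tumors.* The minus may have been lost in extraction, so this cannot be established.
- *The remaining fault is proved for all tumors.* The result at −0.3 rests on the near-diploid, clonal model. It concerns array data only, since the sequencing alternative has no numeric cut-off.
- *Amplified tumors should not be enrolled.* Section 2.2 links CDK4 amplification to relative resistance, but 2.3 calls Rb status the primary determinant of benefit. Including them may be defensible.
- *Wrongly admitted patients diluted Cohort 2's power or explain its low PFS6.* The documents give neither genotype-specific rates nor the share of patients entering by each route.
- *The RB1 wording lets in RB1-mutant tumors.* Criterion 8 separately requires both full RB1 sequencing and an RB1 copy report, under a wild-type requirement.
- *The calendar footnotes are a rival entry rule.* Both refer the reader to section 3, although they omit CDK4/6.

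**Conclusion.** The point holds, as a decision threshold that does not define its own category and as entry routes that disagree between sections. Under either sign the array number admits tumors that the criterion's own words exclude. At +0.3 it admits intact genes. At −0.3 it admits single-copy loss above about 37.5% tumor content, under the stated model. The conflict between criterion 8, 9.1 and 14.1 is plain from the text and rests on no assumption.

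The reach is modest. It touches who may fill the remaining Cohort 1 slots, how the Cohort 1 pharmacodynamic findings are described, and how the Cohort 2 population is labeled. The Cohort 1 primary objective (drug concentration in tumor) and the Cohort 2 operating characteristics are unaffected. The RB1 connective and the calendar footnotes are tidying matters. The text should be corrected while Cohort 1 remains open.

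**What to change.** (a) Check the sign against the source document. Replace the array cut-off with one chosen by the sponsor's molecular pathologists, read against reported tumor content, that excludes single-copy loss. Where tumor content is low or unreported, let the central reviewer decide from raw data. A value near −1.0 at 50% or more tumor content is only a model-based reference with no margin for noise or subclonality, so it should not be adopted unexamined.

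(b) Reconcile criterion 8, 9.1 and 14.1, and the summaries in 1.1 and 2.3, to one list of entry routes for the remaining Cohort 1 slots. The sponsor decides which routes qualify. In the same edit, the RB1 connective could become a plain and, and the calendar footnotes could add CDK4/6.

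(c) Within the molecular-phenotype analysis already planned for Cohort 2, assign each patient's entry route, blind to outcome, from the reports already held. Report counts and PFS6 by route with exact intervals. These can only describe. The reported 9.37% of 32 is 3 successes; if, for example, the split were 24 and 8 with all 3 in the larger group, the exact 95% intervals would be 2.7–32.4% for 3/24 and 0–36.9% for 0/8.

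The cost is wording changes, a re-read of 32 reports and possibly slightly slower Cohort 1 accrual.
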